## 3 STUDY OBJECTIVES

### 3.1 Primary Objective

Assess the feasibility of electronic PROs conducted outside-the-clinic.

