## 5 CRITERIA FOR EVALUATION

### 5.1 Primary Endpoint

Percentage of scheduled outside-the-clinic assessments with at least one of the four PROs fully completed.

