### **6.2 Inclusion Criteria**

1. All genders  $\geq$  2 years of age at time of consent
2. Documentation of a Cystic Fibrosis (CF) diagnosis as evidenced by one or more clinical features consistent with the CF phenotype and one or more of the following criteria:
  - Sweat chloride equal to or greater than 60 mEq/liter by quantitative pilocarpine iontophoresis test (QPIT)

- Two well-characterized mutations in the cystic fibrosis transmembrane conductance regulator (CFTR) gene
- Abnormal nasal potential difference (change in NPD in response to a low chloride solution and isoproterenol of less than -5 mV)

3. Enrolled in the Cystic Fibrosis Foundation Patient Registry (subjects may enroll in the Registry at Enrollment Visit if not previously enrolled)
4. Written informed consent (and assent when applicable) obtained from subject or subject's legal representative
5. Willing to complete questionnaires on mobile device
6. Able to use the Medidata Patient Cloud mobile application for completing the questionnaires

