### 6.4 Study Specific Tolerance for Inclusion/Exclusion Criteria

Subjects who fail to meet one or more of the inclusion criteria or who meet any of the exclusion criteria will not be enrolled in this study. Waivers of any of the above study entry criteria will not be granted.

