### 6.5 Screen Fail Criteria

Any consented patient who is excluded from the study before enrollment is considered a screen failure. All screen failures must be documented with the reason for the screen failure adequately stated. If a subject screen fails prior to enrollment, they can be rescreened if the site staff feels they meet eligibility criteria. Rescreened subjects will have to complete all screening procedures (i.e., data from previous screenings cannot be used).

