### 15.3 Analysis of Primary Endpoint

The primary endpoint is the percentage of scheduled outside-the-clinic assessments with at least one PRO fully completed out of the four questionnaires administered (the PAC-SYM, PAGI-SYM, PAC-QOL and the disease-specific questionnaire). The denominator for the percentage is the expected number of outside-the-clinic assessments (# of enrolled subjects x 3 outside-the-clinic assessments/subject).

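### The primary percentage measures follow-up completion among people already willing and able to use the app; alone, it does not show that ePRO is feasible in people with CF generally

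*Protocol*

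**What the plan says.** Protocol 3.1 sets the primary objective: "Assess the feasibility of electronic PROs conducted outside-the-clinic". Protocol 5.1 turns this into one number: "Percentage of scheduled outside-the-clinic assessments with at least one of the four PROs fully completed". Protocol 15.3 fixes the base: "The denominator for the percentage is the expected number of outside-the-clinic assessments", computed as the number "of enrolled subjects x 3 outside-the-clinic assessments/subject".

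Protocol 6.2 makes two app-related conditions part of eligibility. Criterion 5 is "Willing to complete questionnaires on mobile device" and criterion 6 is "Able to use the Medidata Patient Cloud mobile application for completing the questionnaires". Protocol 6.4 adds that "Waivers of any of the above study entry criteria will not be granted".

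SAP 2.3 adds a third condition. A participant counts as enrolled only if eligible and with one or more of the four ePRO questionnaires answered in full at baseline. The footnotes to Exhibits 1.1 and 2.1 repeat this.

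On people who do not get in, Protocol 6.5 applies to consented patients: "All screen failures must be documented with the reason for the screen failure adequately stated". SAP Exhibit 1.1 counts patients screened, eligible and enrolled by site, without reasons. Exhibit 1.2 is a CONSORT diagram whose boxes are not set out. SAP 3.3 presents the primary percentage overall and by age group and does not refer to anyone outside the enrolled set.

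**The concern.** The quality under study is also a condition of being studied. A patient who will not use a mobile device, cannot operate the app, or finishes no questionnaire on it at the enrollment visit has met ePRO infeasibility in its plainest form. Each of them is outside the denominator, so the percentage can be high however many there are.

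This affects what the trial may conclude. The first sample-size criterion in Protocol 15.7 pairs feasibility with the representativeness of the enrolled subjects, and one secondary objective in Protocol 3.2 is to inform the design of later studies. A reader could easily take the headline figure as the share of assessments that people with CF in general would complete at home. The planned confidence interval would not warn them, because it reflects sampling error among the enrolled only.

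**Working it through.** **Who can enter the denominator.** Following the steps of Protocol 10.1:

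| Stage | Who drops out here | In the primary denominator? | Recorded where |
|---|---|---|---|
| Before consent (step 1) | People who decline when told about the app | No | No log described |
| Eligibility review (step 3) | Consented patients failing criterion 5 or 6 | No | Screen-failure reason (Protocol 6.5) |
| App set-up and baseline questionnaires (steps 8 and 9) | Eligible patients with no ePRO finished at baseline | No, under SAP 2.3 | Eligible minus enrolled in Exhibit 1.1 |
| Follow-up | Enrolled patients who stop answering | Yes, as not completed | Exhibit 3.1 |

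Only the last row can lower the primary percentage.

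**The plan's own figures.** With 400 enrolled, the denominator is 400 x 3 = 1200 assessments. The only sample-size figure stated is about 400, for constipation prevalence, and it reproduces: 1.96² x 0.25 x 0.75 / 0.045² = 355.7, rounded up to 356; 356 / 0.88 = 405, or 356 x 1.12 = 399. It has no bearing on who enters the feasibility denominator. The documents give no expected or target completion percentage.

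**Size, by assumption only.** Let C be completion among the enrolled. Let a be consented patients failing criterion 5 or 6, let b be eligible patients with no completed baseline ePRO, and let s = (a + b) / (enrolled + a + b). If none of these people completes a follow-up assessment, completion over the wider group is C x (1 - s). Neither C nor s is in the documents, so both are varied:

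| Assumed C | s = 5% | s = 10% | s = 20% | s = 30% |
|---|---|---|---|---|
| 70% | 66.5% | 63.0% | 56.0% | 49.0% |
| 88% | 83.6% | 79.2% | 70.4% | 61.6% |
| 95% | 90.25% | 85.5% | 76.0% | 66.5% |

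In head counts with 400 enrolled, a + b = 400 x s / (1 - s): about 21 people for s = 5%, 44 for 10%, 100 for 20% and 171 for 30%.

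**Against sampling error.** At C = 88% and 1200 assessments, the Wilson 95% half-width is about 1.8 points, ignoring clustering within subject. If a subject's three assessments were perfectly correlated, the effective number would be 400 and the half-width about 3.2 points. The shift at s = 5% is 88.0 - 83.6 = 4.4 points, larger than either. On these assumed values, a small loss at entry would outweigh the uncertainty that the report plans to show.

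**The case against.** **The endpoint is a different quantity, and a legitimate one.** It concerns scheduled assessments, and a person never enrolled has none scheduled. Enrolled people who drift away stay in the denominator, and withdrawals are not replaced (Protocol 12.2), so the figure can still turn out poor. A later study run on an app would presumably also enroll willing users, for whom completion among enrollees is a useful planning number. This stands. A reader might infer that the primary percentage is biased or invalid. It is high only relative to a broader feasibility target, which the documents never define.

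**The criteria follow from the design.** Every questionnaire is answered on a mobile device, so someone who cannot use the app supplies no PRO data for the symptom objectives. This stands too, and there is no case for removing the criteria.

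**Much is already reported.** Enrolled subjects are compared with the CF registry (Protocol 15.2, SAP Exhibit 2.1), representation is considered at the interim review (Protocol 15.6), and completion is shown by age group and site. Parents or guardians answer for children under 12. The CONSORT diagram might list reasons for exclusion. A reader might infer that the plan will conceal them; the documents show only that reasons are not specified. However, the registry comparison covers demographic and clinical features, not app use, and nothing links losses at entry to the primary result.

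**A wider denominator has limits.** People unwilling to use a phone may decline before consent and leave no record, so the supplementary figure could sit close to the primary one and falsely reassure. Protocol 6.5 requires a reason for failure, not a check of every other criterion, so it may be unclear whether a patient was otherwise eligible. The figure also mixes entry failure with follow-up completion. All of this is fair, and it is why the figure can only be a labelled sensitivity result.

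**Conclusion.** The point holds as one of interpretation and reporting. The primary percentage estimates follow-up completion among people who were willing and able to use the app and, under SAP 2.3, had already finished at least one questionnaire on it. It does not by itself estimate the feasibility of ePRO in people with CF generally.

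The size of the gap cannot be derived. The tabulated values, such as 88% falling to 83.6% or 70.4%, rest on assumed completion, an assumed loss at entry, and no follow-up completion among those lost. They show that the gap could exceed sampling error, not that it does.

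A reader might also infer that the result will decide whether later CF studies rely on home ePRO. The documents state no such rule and no feasibility threshold; they say only that the study should inform future designs. The point is worth acting on because the remedy is cheap and affects the wording of the main conclusion. It does not undermine the design.

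**What to change.** Keep criteria 5 and 6 and the primary endpoint as they are, and make these changes in the SAP and report:

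1. In Exhibits 1.1 and 1.2, report overall and by age group (a) consented patients whose documented screen-failure reason is criterion 5 or 6, and (b) eligible patients with no fully completed baseline ePRO. Count each person once, and leave anyone rescreened and later enrolled among the enrolled.
2. In SAP 3.3, beside the primary percentage, give a sensitivity percentage with denominator (enrolled + a + b) x 3, counting any assessment without a completed PRO as not completed.
3. State that this figure is still an upper bound, because refusals before consent are not captured.
4. Word the primary conclusion as completion among patients willing and able to use the app.

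The cost is a few table rows and some wording. Sites must already document the reasons, and group (b) is already implied by Exhibit 1.1. The documents do not say whether reasons are coded by criterion, so sorting them may take some work. The downside is a less favourable supplementary figure that combines entry failure with follow-up completion. It should be labelled as a sensitivity result and should not replace the primary percentage.

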### 6.3 Exclusion Criteria

1. Presence of a condition or abnormality that, in the opinion of the Investigator, would complicate interpretation of study outcome data or interfere with achieving the study objectives
2. Presence of a pulmonary exacerbation at the Enrollment Visit
3. Hospitalization for distal intestinal obstruction syndrome (DIOS) within the 28 days prior to the Enrollment Visit
4. Current gastrointestinal (GI) or abdominal/pelvic malignancy
5. Abdominal or pelvic surgery within the 28 days prior to the Enrollment Visit
6. At the time of the Enrollment Visit, planned abdominal or pelvic surgery or bowel cleanout in the 28 days after the Enrollment Visit.
7. Initiation of new CFTR modulator therapy within the 4 weeks prior to the Enrollment Visit
8. Intent to initiate new CFTR modulator therapy within 28 days of the Enrollment Visit

### 6.4 Study Specific Tolerance for Inclusion/Exclusion Criteria

Subjects who fail to meet one or more of the inclusion criteria or who meet any of the exclusion criteria will not be enrolled in this study. Waivers of any of the above study entry criteria will not be granted.

### 6.5 Screen Fail Criteria

Any consented patient who is excluded from the study before enrollment is considered a screen failure. All screen failures must be documented with the reason for the screen failure adequately stated. If a subject screen fails prior to enrollment, they can be rescreened if the site staff feels they meet eligibility criteria. Rescreened subjects will have to complete all screening procedures (i.e., data from previous screenings cannot be used).

## 7 CONCURRENT MEDICATIONS

### 7.1 Allowed Medications and Treatments

Standard therapy for CF is allowed.

## 7.2 Prohibited Medications and Treatments

There are no prohibited medications.

## 8 STUDY TREATMENTS

Not applicable.

## 9 STUDY PROCEDURES AND GUIDELINES

The procedures described below will be performed at the visits noted in the Schedule of Events (Appendix) and in Section 9.

Prior to conducting any study-related activities, written informed consent and the Health Insurance Portability and Accountability Act (HIPAA) authorization must be signed and dated by the subject or subject's legal representative. If appropriate, assent must also be obtained prior to conducting any study-related activities.

### 9.1 Clinical Assessments

#### 9.1.1 Concomitant Medications

Concomitant medications and concurrent therapies will be documented as noted in the Schedule of Events.

#### 9.1.2 Demographics and CFF Registry ID

Demographic information (date of birth, sex, race) and CF Registry number will be recorded.

#### 9.1.3 Medical History

Relevant medical history, including history of current disease, other pertinent gastrointestinal history, and information regarding underlying diseases will be recorded.

#### 9.1.4 CF Diagnosis

CF diagnostic test date(s) and results will be recorded.

#### 9.1.5 Weight and Height

Weight will be measured and recorded as noted in the Schedule of Events. Adults and children may remain in clothes (without shoes). A standing height will be measured and recorded as noted in the Schedule of Events.

#### 9.1.6 Subject Questionnaire: Patient Assessment of Gastrointestinal Disorders – Symptom Severity Index (PAGI-SYM)

Subjects will complete the PAGI-SYM questionnaire as noted in the Schedule of Events. The PAGI-SYM questionnaire measures specific symptoms of patients with upper gastrointestinal disorders, specifically GERD, dyspepsia and gastroparesis. The PAGI-SYM contains 20 questions scored on a 6-point Likert response scale (0 – 5 range). The questionnaire takes approximately 5 minutes to complete. For subjects  $\geq$  2 years of age to < 12 years of age, the

parent/guardian will complete the questionnaire. For subjects  $\geq 12$  years of age, the subject will complete the questionnaire.

### **9.1.7 Subject Questionnaire: Patient Assessment of Constipation – Symptom Severity Index (PAC-SYM)**

Subjects will complete the PAC-SYM questionnaire as noted in the Schedule of Events. The PAC-SYM questionnaire measures specific symptoms of patients with constipation. The PAC-SYM contains 12 questions scored on a 5-point Likert response scale (0 – 4 range). The questionnaire takes approximately 5 minutes to complete. For subjects  $\geq 2$  years of age to  $< 12$  years of age, the parent/guardian will complete the questionnaire. For subjects  $\geq 12$  years of age, the subject will complete the questionnaire.

### **9.1.8 Subject Questionnaire: Patient Assessment of Constipation Quality of Life (PAC-QOL)**

Subjects will complete the PAC-QOL questionnaire as noted in the Schedule of Events. The PAC-QOL questionnaire measures quality of life of patients with constipation. The PAC-QOL contains 28 questions scored on a 5-point Likert response scale (0 – 4 range). The questionnaire takes approximately 5 minutes to complete. For subjects  $\geq 2$  years of age to  $< 12$  years of age, the parent/guardian will complete the questionnaire. For subjects  $\geq 12$  years of age, the subject will complete the questionnaire.

### **9.1.9 Disease-specific questions**

The Bristol Stool Scale is a visual assessment of stool consistency. In addition, there are questions related to stool quality, frequency and presence of fecal incontinence. These will be completed as noted in the Schedule of Events. The questionnaire takes approximately 5 minutes to complete. For subjects  $\geq 2$  years of age to  $< 12$  years of age, the parent/guardian will complete these questions. For subjects  $\geq 12$  years of age, the subject will complete these questions.

## **10 EVALUATIONS BY VISIT**

### **10.1 Enrollment Visit (Day 1)**

1. Review the study with the subject (subject's legal representative) and obtain written informed consent and HIPAA authorization and assent, if appropriate.
2. Assign the subject a unique screening number.
3. Perform review of eligibility criteria.
4. Record demographics data and CFF Registry ID.
5. Record medical history, including a history of CF, diagnosis date, gastrointestinal history, and prior CF and gastrointestinal treatments.
6. Record concomitant medications.
7. Measure and record height and weight.

8. Assist with downloading and registering the Medidata Patient Cloud mobile application for completing the questionnaires into subject's mobile device (e.g., smartphone or tablet computer). Review and provide the subject with the application and questionnaire completion instructions.
9. Complete electronic PRO questionnaires (PAGI-SYM, PAC-SYM, PAC-QOL, and additional disease-specific questions) on mobile device (subject or their parent/guardian).

## **11 ADVERSE EXPERIENCE REPORTING AND DOCUMENTATION**

Adverse Events, including Serious Adverse Experiences, will not be collected as part of this study.

## **12 DISCONTINUATION AND REPLACEMENT OF SUBJECTS**

### **12.1 Early Withdrawal of Subjects from the Study**

All subjects are free to withdraw from participation at any time, for any reason, specified or unspecified, and without prejudice. This may include subjects who withdraw from completing the study visit and who decline to complete the questionnaires.

If the investigator is able to provide a reason for early subject withdrawals, it will be specified in the subject's source documents.

### **12.2 Replacement of Subjects**

Subjects who withdraw from the study will not be replaced.

## **13 PROTOCOL VIOLATIONS**

A protocol violation occurs when the subject, investigator, or the Sponsor fails to adhere to significant protocol requirements affecting the inclusion, exclusion, subject safety and primary endpoint criteria. Protocol violations for this study include, but are not limited to, the following:

- Failure to meet inclusion/exclusion criteria
- Failure to comply with Good Clinical Practice (GCP) guidelines will also result in a protocol violation.

When a protocol violation occurs, it will be discussed with the investigator and a Protocol Violation Form detailing the violation will be generated. This form will be signed by a Sponsor representative and the Investigator. A copy of the form will be filed in the site's regulatory binder and in the Sponsor's files. The site will report the violation to their IRB in accordance with their IRB reporting requirements.

## **14 DATA SAFETY MONITORING**

Not applicable

## 15 STATISTICAL METHODS AND CONSIDERATIONS

### 15.1 General Considerations

Prior to the analysis of the final study data, a detailed Statistical Analysis Plan (SAP) will be written, describing all analyses that will be performed. The SAP will contain any modifications to the analysis plan described below.

The endpoints of this study are mostly descriptive, with all continuous outcomes such as symptom severity and PRO scores evaluated using descriptive statistics such as mean, median, standard deviation and 95% confidence intervals. Presence/absence of symptoms will be shown as percentages and corresponding 95% confidence intervals calculated using the Wilson method. Group comparisons will be made via the two-sample t-test for continuous outcomes or Fisher's exact test for categorical outcomes. Except where otherwise noted, all tests will be two-sided and statistical significance will be determined at the 0.05 level. No adjustment for multiple comparisons will be made.

#### 15.1.1 Data Sets Analyzed

The analysis population consists of all eligible subjects who enroll into the study – the Full Analysis Set. For select endpoints, stratification of study results by age group, CF genotype, pancreatic status, and whether sites were DIGEST awardees will also be considered.

### 15.2 Demographic and Baseline Characteristics

The enrolled study population will be described with respect to baseline demographic and clinical characteristics such as age, gender, race, ethnicity, genotype, height, weight, pancreatic status, body mass index, and use of concomitant medications. Demographics of subjects comparing completers (those who completed all questionnaires at all assessments) to those that are not completers will also be included. To evaluate the representativeness of the enrolled study population, the demographics of enrolled subjects will be compared against the general CF population (from the CFF Patient registry).

### 15.3 Analysis of Primary Endpoint

The primary endpoint is the percentage of scheduled outside-the-clinic assessments with at least one PRO fully completed out of the four questionnaires administered (the PAC-SYM, PAGI-SYM, PAC-QOL and the disease-specific questionnaire). The denominator for the percentage is the expected number of outside-the-clinic assessments (# of enrolled subjects x 3 outside-the-clinic assessments/subject).

### 15.4 Analysis of Secondary Endpoints

Constipation is defined as <3 bowel movements in the past week and/or Bristol Stool type 1 or 2. The secondary endpoint upon which the sample size is based is the number (%) of enrolled subjects with any occurrence of constipation during 1 month of follow-up (the period prevalence). Treatment for GI symptoms and constipation will be summarized based on the percentage of enrolled subjects receiving and initiating treatment at time of enrollment visit. To evaluate whether CF subjects are adequately treated, the number and percentage of subjects with GI symptoms and constipation on treatment will be reported. All GI related treatments will be classified by medication type/class.

Individual GI symptoms will be extracted from the PAC-SYM and PAGI-SYM questionnaires. For each GI symptom, frequency and severity will be summarized at each assessment as follows: number (%) of subjects with GI symptom, severity of GI symptom (mean score and distribution of severity score) and change in severity scores from the enrollment visit by whether subjects were receiving treatment.

Mean overall (and by sub-scale) PRO scores for PAC-SYM, PAGI-SYM and PAC-QOL at scheduled assessments will be reported including evaluation of within and between subject variability. Group comparisons of mean scores by subjects receiving/not receiving treatment and by those with/without constipation will also be made. Absolute change in PRO scores from enrollment visit to scheduled assessments will be reported based on subjects receiving/not receiving treatment for constipation. To examine these effects, figures displaying mean PRO scores by scheduled assessment will be created. Additionally, mixed effects models for repeated measures will be fit with PRO scores as the outcome and covariates for visit, treatment, pancreatic status, age group and the interaction between treatment and visit.

Alternative definitions of constipation that are CF specific will be created based on different frequencies of bowel movement and Bristol stool type evaluated individually or in combination. Spearman correlations of stool frequency with the PAC-SYM score and Bristol stool type with PAC-SYM scores will be examined. The different constipation definitions will be evaluated by comparing against the area under the curve of receiver operating characteristic curve (ROC curve) for PAC-SYM scores. The percentage of subjects reporting constipation based on self-assessment and the concordance to the protocol definition/alternate definitions will be made using Cohen's kappa coefficient.

